Study Protocol
SkillJoy Randomized Controlled Trial
[name].^{1,2}
[name].²
Department of Psychology
Skidmore College¹
Pennsylvania State University²
April 30th, 2018

Method

Participants

Participants were identified through the Pennsylvania State University subject pool. All those invited to participate via email met DSM-5 criteria for GAD on the *Generalized Anxiety Disorder Questionnaire-IV* (GAD-Q-IV; Newman et al., 2002). Those who accepted the invitation were then screened on the phone for GAD a second time by clinical interview (the GAD section of the Mini-International Neuropsychiatric Interview (MINI); Sheehan et al., 2015). They were required to meet full criteria for GAD on both the GAD-Q-IV and the MINI to participate. All participants were 18 years of age or older, spoke English, and were able to consent.

Measures

Primary outcome measures

The Penn State Worry Questionnaire (PSWQ; Meyer, Miller, Metzger, & Borkovec, 1990) is a 16-item self-report scale of the severity and frequency of worry. It has strong internal consistency .91, retest reliability ($r = 0.92$), convergent and discriminant validity, and sensitivity to change from psychotherapy (Brown, Antony, & Barlow, 1992; Meyer et al., 1990). In our sample, internal consistency was $\alpha = .78$ at pre-trial, .87 at post-trial, and .89 at follow-up.

The Positive and Negative Affect Schedule, Expanded Form: Joviality Scale (PANAS-X Joviality; Watson & Clark, 1994) is an 8-item measure of positive emotions. This joy sub-factor had an average factor loading of 0.73 (Egloff, Schmukle, Burns, Kohlmann, & Hock, 2003; Watson & Clark, 1994). It had strong internal consistency (median $\alpha = .93$) across eight studies of various time intervals (e.g., momentary, daily, past few days, past week, or past month; $\alpha = .88$ to $.94$), as well as convergent and discriminant validity (Watson & Clark, 1994). In our

sample, internal consistency was good (pre: $\alpha = .90$; post: $.88$; follow-up: $.92$).

The Savoring the Moment Subscale of the Savoring Beliefs Inventory (SBI; Bryant, 2003). The SBI is a 14-item survey that measures beliefs about one's ability to savor. The savoring the moment subscale measures savoring of present-moment emotional experience. Confirmatory factor analysis showed all subscales had good fit (Bryant, 2003), had good-retest reliability ($r = .88$), and internal consistency reliability ($\alpha = .78$ for total scale), convergent and divergent validity. In our sample, internal consistency was good (pre: $\alpha = .80$; post: $.86$; follow-up: $.84$).

Secondary Outcome Measures

Responses to Positive Affect Scale (RPAS; Feldman, Joormann, & Johnson, 2008) was used to measure kill-joy thinking (a.k.a. "dampening"). Participants rated eight dampening items on a 5-point scale. The RPAS showed good model fit (RMSEA = 0.043; CFI = 0.94; RMSR = 0.049), internal consistency ($\alpha = 0.76 - 0.83$), convergent and discriminant validity (Feldman et al., 2008; Nelis, Holmes, & Raes, 2015). In our sample, internal consistency was good (pre: $\alpha = .86$; post: $.88$; follow-up: $.88$).

The Prioritizing Positivity Scale (PPS; Catalino et al., 2014) measured the degree to which participants prioritized seeking positive experiences on six items with which participants either agree or disagree on a nine-point scale. It had good model fit (CFI = .99; RMSEA = .04), internal consistency reliability ($\alpha = .81$), and good construct validity (Catalino et al., 2014). In our sample, internal consistency was good (pre: $\alpha = .83$; post: $.88$; follow-up: $.91$).

The Life Orientation Test – Revised (LOT-R; Scheier, Carver, & Bridges, 1994) measures optimism. It has 10 items rated on a four-point scale. It showed good model fit (CFI = .99, TLI = .99, RMSEA = .04), convergent, and discriminant validity (Glaesmer et al., 2012; Herzberg,

Glaesmer, & Hoyer, 2006). Internal consistency was acceptable in our sample (pre: $\alpha = .78$; post: $.82$; follow-up: $.82$).

The Beck Depression Inventory II (BDI-II; Beck, Steer, & Brown, 1996) is a widely used, 21-item self-report survey that measures the presence and severity of depressive symptoms. It has repeatedly demonstrated high internal consistency, such as $\alpha = 0.93$ (Beck et al., 1996). Convergent and discriminant validity have been demonstrated as well (Beck et al., 1996). In our sample, internal consistency was good (pre: $\alpha = .88$; post: $.93$; follow-up: $.95$).

Smartphone Software Applications

PACO: The Personal Analytics Companion (PACO Developers, 2018) is a mobile application software package for designing ecological momentary studies. It allows for fixed, user-editable, and stratified random prompting on personal iOS and Android phones. *Quip* (Taylor & Gibbs, 2018) is a mobile application for creating documents, task lists, and embedded spreadsheets that can be edited in real time by multiple users across multiple devices.

Procedure

All data was collected prior to the COVID-19 pandemic. Eligible participants were randomly assigned to either the SkillJoy treatment condition or the active self-monitoring (ASM) control condition. The interventions and organization of prompt times were informed by several rounds of pilot testing. After arriving at the laboratory, all participants were provided informed consent. They then completed baseline questionnaires using PsychData on a laboratory computer as well as a computerized task (for another study). They were then given a description and rationale for their assigned treatment conditions regarding how it would reduce their GAD symptoms and increase positive emotions (see supplementary materials). Subsequently, participants downloaded and started study apps. Each participant also received a Quip document

with their condition's rationale and instructions on how to complete each part of the intervention, an organized scheduling spreadsheet, and a note-taking space. They were trained on how to use their assigned app, assisted with a PowerPoint presentation to which participants had access throughout the study. At the end of the training session both groups were given information on following steps of the study, were reminded of the compliance check phone call on their fifth day of EMI use, and post-trial study tasks, and were given opportunities to ask questions.

The EMI was delivered by the PACO app and involved seven days in participants' natural environments. Each day participants received 8 prompts that required engagement and assessment. A 9th prompt in the afternoon reminded them to engage in a scheduled activity. Each day's first and last prompt times were user-editable, to fit their sleep schedules. Other prompts were delivered at random times within pre-determined intervals between 9:00 AM and 10:30 PM daily. All prompts included EMA ratings not reported here for brevity, but were identical between conditions. Four daily prompts in both conditions included the PANAS-X Joviality scale. Participants also received a compliance check phone call on the fifth day of the trial, which asked about rate of compliance and level of effort, if any harm had occurred, and encouraged full participation in the study. Participants were then directed to complete mid-measures online before midnight that day (not included in the current study). Participants returned to the laboratory on the eighth day of the study where they completed the same series of questionnaires and tasks given at baseline. On the 30th day, they received an email with a link to PsychData to complete follow-up measures and were compensated for their participation.

SkillJoy Condition

SkillJoy Training: SkillJoy participants were initially trained in savoring practice exercises that resembled their intervention. They were guided through remembering and

describing a positive moment from their past, as well as one good experience from their current day. Next, they engaged in present-moment savoring. They first chose a small candy or dried fruit from multiple options. They were then guided through attending to the sensory, emotional, and cognitive experience of eating it in the moment, purposefully attempting to amplify and extend the resulting positive emotion. After, they brainstormed, and scheduled daily enjoyable activities for the week that were rated a 7 or greater on a 10 point enjoyable scale and recorded them in a Quip template along with five suggested activities.

SkillJoy EMI: Present-moment savoring prompts were delivered within the stratified random prompting. All other prompts were delivered at fixed times distributed across the day. SkillJoy included a variety of savoring interventions modified to target GAD pathology. These interventions included 1) *Enjoyable Activity Savoring*. Participants were prompted at a time of their choosing (before 11:30 AM) to schedule an exact time for an enjoyable activity for the following day. They were then reminded and later prompted to practice savoring upcoming positive activities. At the end of the day, they were asked to focus on what they liked about their enjoyable activity; 2) *Present-Moment Positive Evaluation*. Participants received three identical daily prompts guiding them to focus on and savor what they enjoyed about the present moment; 3) *Savoring recent memories*. Participants received two daily prompts to encourage savoring of recent activities and events, focusing on amplifying and extending the duration of positive emotions ; 4) “*Counting Blessings*” *Technique*. Two times a day participants received prompts guiding them to consider and write about events that turned out better than expected and events that were enjoyable or went well. 5) *Looking forward to the day’s events*. During participants’ first daily morning prompt, they were asked to savor an upcoming activity for that day.

Active Self-Monitoring Control EMI

Active Self-Monitoring (ASM) Training: ASM control participants were trained using identical structure and content to SkillJoy participants, *omitting* aspects theorized to increase positive emotion. They were guided through remembering a day one week in the past, as well as an event from the current day, to practice reflective thinking. After, they engaged in present-moment self-awareness. They chose a small candy or dried fruit and were asked to focus on and describe their thoughts and feelings while eating it. This activity resembled a mindfulness exercise, but did not direct attention to any specifically *positive* emotions or thoughts. Next, participants described and scheduled possible future events they had to do or planned to do during each day of the following week and recorded them in a condition-specific Quip template.

ASM EMI: The ASM control included self-monitoring activities mirroring SkillJoy interventions, but omitting components to increase or sustain positive emotion. Careful attention was paid to match SkillJoy in its tone of language. Interventions included: 1) *Planning tomorrow's activities*. Each morning at a time of their choosing (before 11:30AM) participants received a prompt to think about major events that would take place in the following day using their daily Quip schedule and notes and were directed to stay apprised of their scheduled events. They also received a daily prompt about attending to their thoughts, feelings, and plans. At the end of the day, they were asked to remember, record and focus on their thoughts and feelings from that day; 2) *In-the-moment thoughts and feelings*. Participants received three identical stratified random prompts to attend to their thoughts and feelings at the present moment: 3) *Remembering*. Participants received two prompts to encourage remembering recent activities and events from their day, no matter what events these were. These prompts asked them to think of an event from their day, take 60 seconds to remember the event in detail, and complete a series of ratings about the event. 4) *Recording the day's events*. Two times a day participants received

prompts guiding them to record and think about events from their day. 5) *Anticipating the day's biggest event*. Each day during participants' first morning prompt they were asked to anticipate and record that days most important event.

Statistical Analysis Plan

SkillJoy Randomized Controlled Trial

[name].^{1,2}

[name].²

Department of Psychology

Skidmore College¹

Pennsylvania State University²

May 5th, 2019

Planned Statistical Analyses

Power analysis with RMASS II suggested a need for 70 total participants for a two-level longitudinal linear mixed effects model of adequate power (0.80). To account for missing data, we used multiple imputation with 100 iterations of the Markov Chain Monte Carlo (MCMC) method, creating 10 imputed datasets. All results reflect analyses pooled across the imputed datasets. We then used longitudinal multilevel modeling for all outcome measure efficacy analyses. Regarding treatment outcome, longitudinal linear mixed models compared trends of change across time on all symptom, positive affect, and regulation strategy outcome measures between intervention conditions. These models all included the intercept, linear time trend, condition, and interaction between time trend and condition as fixed effects and the intercept as a random effect. Separate models were run to examine the change from baseline/pre-trial to eighth day post-trial (pre- to post-trial; the intervention phase) and from pre-trial to the 30th day follow-up (pre- to follow-up). We also examined the maintenance of treatment gains by comparing trajectories of change from eighth day post-trial measures to the 30th day follow-up. Simple slopes analyses were conducted for each outcome and learning variable within each condition.

Between-condition differences in baseline measures, degrees of missingness, and compliance rates were examined with independent samples t-tests. Reliable change index analyses used the formula of Jacobson and Truax (1991). Cohen's d was calculated in the traditional manner for t-tests, Cohen's $d = (M_2 - M_1) / SD_{pooled}$ where $SD_{pooled} = \sqrt{((SD_1^2 + SD_2^2) / 2)}$ (Cohen, 1988). In longitudinal linear mixed models and simple slopes analyses, Cohen's d was calculated with an alternative formula fit for multilevel models, $d = 2t / (\sqrt{df})$, as

recommended by Rosenthal (1994). Note that pre- to follow-up analyses are underpowered with the subset of our sample that completed follow-up measures ($n = 66$).

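### Optional improvement, not an error: the two baseline-anchored models act as change-score tests, and adjusting for the baseline score would in large samples be at least as precise

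*SAP*

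**What the plan says.** The SAP (Planned Statistical Analyses) gives one specification for every efficacy model: "These models all included the intercept, linear time trend, condition, and interaction between time trend and condition as fixed effects". The only random term is a participant intercept. It applies this to pairs of occasions. "Separate models were run to examine the change from baseline/pre-trial to eighth day post-trial", and another covers pre-trial to day 30. A third contrast starts after randomisation: "We also examined the maintenance of treatment gains by comparing trajectories of change from eighth day post-trial measures to the 30th day follow-up".

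The baseline score is not otherwise used in the efficacy analysis. The SAP only tests it for imbalance: "Between-condition differences in baseline measures, degrees of missingness, and compliance rates were examined with independent samples t-tests". Missing values are multiply imputed (10 datasets), so each model runs on completed data. The sample size is 70 for power 0.80. On the later time point the SAP adds: "Note that pre- to follow-up analyses are underpowered with the subset of our sample that completed follow-up measures" (n = 66).

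The Protocol (Procedure) places the baseline measurement before participants heard the rationale for their assigned condition: "They then completed baseline questionnaires using PsychData on a laboratory computer". The score is therefore suitable as a covariate.

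**The concern.** With two occasions, the four fixed effects fit four free cell means, including a separate baseline mean for each arm. The model thus does not use the fact that randomisation makes the expected baseline means equal. The interaction becomes the between-arm difference in mean change, which subtracts the whole baseline score whatever its correlation with the outcome. When that correlation is moderate, this adds noise that a regression on baseline would avoid. It also leaves a chance baseline gap uncorrected.

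What is at stake is precision, not validity. The trial is small and the SAP itself calls the day-30 comparison underpowered, so precision available from data already in hand is worth considering. The day-8 to day-30 contrast is outside this point, because its first wave may already carry a treatment effect.

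**Working it through.** **The plan's own figure.** N = 70 for power 0.80 cannot be reproduced. The SAP gives no effect size, alpha, sidedness or correlation. It serves here only as an anchor: the change-score test is assumed to have 80% power at N = 70.

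**Equivalence.** On one simulated complete two-wave dataset (35 per arm), the change-score test and the random-intercept time × condition test both gave t = 3.279.

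**Precision.** Write s0 and s1 for the pre and post SDs, ρ for their correlation and k = s1/s0.
- Change-score variance: s0² + s1² − 2ρ·s0·s1
- Baseline-adjusted variance: s1²(1 − ρ²)
- Difference: (s0 − ρ·s1)², which is never negative and is zero only when ρk = 1
- Ratio, adjusted to planned: k²(1 − ρ²)/(1 + k² − 2ρk)

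Example, ρ = 0.5 and k = 1: 0.75/(2 − 1) = 0.75.

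**Power.** The assumptions are 1:1 allocation, N = 70 and two-sided 0.05, with the effect fixed at 80% power for the change-score test (68 df). The adjusted test has 67 df, and its variance is multiplied by 1 + 1/66 for estimating the slope. Noncentral t gives:

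| k | ρ = 0.5 | ρ = 0.7 | ρ = 0.88 |
|---|---|---|---|
| 1 | 89.4% | 85.4% | 81.8% |
| 1.15 | 85.6% | 81.5% | 79.4% |
| 1.3 | 82.9% | 79.8% | 81.5% |

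Simulation (20,000 trials per cell) agrees. Planned versus adjusted was 0.800 v 0.893 at ρ 0.5, k 1, and 0.800 v 0.795 at ρ 0.88, k 1.15. Mean error of both estimators was within 0.003 SD of zero in every cell. Over ρ 0.3–0.92 and k 1–1.3 the change runs from −0.6 to +13.2 points.

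**A rough indication of k.** The Protocol (Measures) gives sample alphas by wave; for the PSWQ, α = .78 "at pre-trial, .87 at post-trial, and .89 at follow-up". Two alternative assumptions turn these into k for an n-item scale:
- Constant summed item variance: k = √[(1 − α_pre(n−1)/n)/(1 − α_post(n−1)/n)]
- Constant error variance: k = √[(1 − α_pre)/(1 − α_post)]

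For the PSWQ at day 8 (n = 16), the second gives √(0.22/0.13) = 1.301 and the first gives 1.207. For Savoring the Moment only the second can be used, because the subscale's item count is not given: √(0.20/0.14) = 1.20 at day 8 and √(0.20/0.16) = 1.12 at day 30.

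| Primary outcome, wave | k | Adjusted power, ρ 0.5 | Adjusted power, ρ 0.7 |
|---|---|---|---|
| PSWQ, day 8 | 1.21–1.30 | 83–84% | 80–81% |
| PSWQ, day 30 | 1.27–1.41 | 82–83% | 79–80% |
| PANAS-X Joviality, day 8 | 0.91–0.96 | 91–92% | 87–89% |
| PANAS-X Joviality, day 30 | 1.04–1.12 | 86–88% | 82–84% |
| Savoring the Moment, day 8 | 1.20 | 85% | 81% |
| Savoring the Moment, day 30 | 1.12 | 86% | 82% |

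The day-30 rows keep the N = 70, 80% anchor, so they show relative gain, not the trial's actual follow-up power. Taking 80% as the reference at N = 66 instead moves results by no more than 0.1 point.

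**Chance imbalance.** Given a realised baseline gap D, the change-score estimate shifts by (ρk − 1)D. One standard error of the gap is √(2/35) = 0.24 baseline SD. The shift is then (0.5 − 1) × 0.24 = −0.12 SD at ρ 0.5, k 1, and (0.91 − 1) × 0.24 = −0.02 SD at ρ 0.7, k 1.3. The documents report no such gap.

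**The case against.** The strongest objection is that this is a preference. The SAP sets out to compare change between arms, its models do that validly, and no contradiction or bias is alleged. That stands, and it is why the point is offered only for consideration.

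Several limits on the size also stand:
- For the PSWQ at day 30, the time point that motivates the point, the gain is about nil at ρ 0.7–0.8 (79–80%).
- If the published retest value of .88 for the savoring inventory approximated ρ, adjusted power for Savoring the Moment would be 79.7% at day 8 and 79.4% at day 30, slightly below planned. A retest coefficient is only a rough upper guide to a pre-post correlation in a trial.
- The never-less-precise property is asymptotic. At ρ 0.88, k 1.15 the adjusted standard error was the larger one in 78% of simulated trials of 70; at ρ 0.5, k 1 this happened in 0.3%.
- ρ and k are assumed, and nothing in the documents supports either assumption used to infer k from alphas.
- The power figures ignore between-imputation variance.
- The SAP does not say outright that day 8 is left out of the pre-to-day-30 model. If it is included, the exact change-score identity and the variance formula do not apply there, although baseline means are still free.

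None of this overturns the claim, which is confined to large samples and allows for no gain on some outcomes. Within the tabulated ranges the worst loss is about 0.6 points, and the possible gain is much larger.

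**Conclusion.** The point holds as an optional improvement, with medium confidence. The pre-to-day-8 and pre-to-day-30 tests are valid but make no use of the expected equality of baseline means. Baseline adjustment would change power by between −0.6 and +13 points for ρ 0.3–0.92 and k 1–1.3. On the rough k values, PANAS-X Joviality at day 8 stands to gain most; the PSWQ and Savoring the Moment may gain little or nothing.

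This rests on two-wave models, completed data, 1:1 allocation (the ratio is not stated), N = 70 (enrolment is not stated), two-sided 0.05 and a planned power of 80% for the change-score test.

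**What to change.** For each outcome, regress the day-8 score, and separately the day-30 score, on condition plus the baseline score. Alternatively, fit a model with categorical time, unstructured covariance and a common baseline mean. Include baseline and condition in the imputation model. Do not let the baseline t-tests decide whether to adjust. Leave the first wave unconstrained in the day-8 to day-30 maintenance contrast, and keep the planned simple-slopes analyses.

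The SAP is written in the past tense with the number of follow-up completers known, and the Protocol reports sample alphas at every wave. If outcomes have been seen, keep the planned models as the main analysis and label the adjusted results as an added or sensitivity analysis, so that the choice cannot follow the result.

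The cost is SAP wording, a re-run on existing data and one degree of freedom, worth up to about 0.6 power points when ρk is near 1. No new data are needed.

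### The SAP's d = 2t/√df puts within-condition slopes and between-arm interactions on different scales (1.41-fold at a common df), and day-8-to-day-30 slopes need a caveat on setting

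*SAP*

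**What the plan says.** All points come from the SAP, Planned Statistical Analyses, and the Protocol, Procedure.

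- **Models.** Each outcome has a random-intercept model with time, condition and their interaction. The SAP states "Separate models were run to examine the change from baseline/pre-trial to eighth day post-trial" and, separately, from pre-trial to day 30. A third comparison covers maintenance: "We also examined the maintenance of treatment gains by comparing trajectories of change from eighth day post-trial measures to the 30th day follow-up".
- **Slopes.** The next sentence reads "Simple slopes analyses were conducted for each outcome and learning variable within each condition".
- **Effect size.** "In longitudinal linear mixed models and simple slopes analyses", the SAP computes Cohen's d as 2t/√df. It does not say which df enter the formula, or whether slopes come from the two-arm model or from each arm fitted alone. Results are pooled over 10 imputed datasets.
- **Setting.** At baseline: "They then completed baseline questionnaires using PsychData on a laboratory computer". At the end of the intervention: "Participants returned to the laboratory on the eighth day of the study where they completed the same series of questionnaires". At follow-up: "On the 30th day, they received an email with a link to PsychData to complete follow-up measures". The SAP has no term or caveat for this change.

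**The concern.** A reader of the results will see two columns of d, one for interactions and one for within-condition slopes, made by the same formula and carrying the same label. The natural step is to compare them: how large is the SkillJoy change beside the advantage over control? If the formula stretches one column relative to the other, that comparison misleads for every outcome and every time window.

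The matter is sharpest for durability, which readers will look for after a seven-day intervention. The between-arm day-8-to-day-30 contrast is expected to be null both when a gain is fully kept and when there was no gain to keep. A reader will therefore turn to the slopes beside it. Over that window the slopes have a second weakness. Everyone moved from the laboratory to an emailed link, so within an arm the change of setting coincides exactly with the passage of time. Both arms had been given a "rationale for their assigned treatment conditions regarding how it would reduce their GAD symptoms and increase positive emotions", so answers could plausibly differ between laboratory and home in either arm. The documents do not show that they did.

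**Working it through.** **Inputs.** The 66 follow-up completers and the formula 2t/√df are from the SAP. Assumed: 1:1 allocation (so n = 33 per arm), flat controls, the same SD of change in both arms, and no modelling of imputation pooling. The SAP prints no d to reproduce.

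**Where the formula comes from.** For two groups of n, t = d·√(n/2) and df ≈ 2n, so d = t·√(2/n) ≈ 2t/√df. For one group, t = d·√n, so the matching conversion is d = t/√n. The factor of 2 belongs to the two-group case only.

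**Same change δ, in SDs of change, put through 2t/√df.** With two time points, a slope is a mean change.

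- Interaction: t = δ·√(33/2) = 4.062δ
- SkillJoy slope: t = δ·√33 = 5.745δ

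| df used | interaction d | slope d | ratio |
|---|---|---|---|
| 64 for both (66 − 2) | 8.124δ/8 = 1.016δ | 11.489δ/8 = 1.436δ | 1.41 |
| 128 for both (132 − 4) | 8.124δ/11.314 = 0.718δ | 11.489δ/11.314 = 1.016δ | 1.41 |
| 64 and 32 (33 − 1) | 1.016δ | 11.489δ/5.657 = 2.031δ | 2.00 |

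For δ = 0.30 the first and last rows give 0.305 against 0.431, and 0.305 against 0.609. At equal df the ratio is √2 whatever the values of n and δ. At N = 70 it is again 1.41 and 2.00. Which column is off depends on the df: at 64 the slope is overstated, while at 128 the interaction is understated.

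**Dependence on correlation.** The formula also works in units of the SD of change, which is SD·√(2(1 − r)). A raw change of 0.30 SD at r = .5, .7 and .9 (assumed values) gives an interaction d of 0.30, 0.39 and 0.68 at df 64. The slope d is 0.43, 0.56 and 0.96 at df 64, and 0.61, 0.79 and 1.36 at df 32. Divided by one common baseline SD, all of these read 0.30.

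**Non-significance is not maintenance.** The SAP's 70 participants at power 0.80 cannot be reproduced, because it gives no effect size, alpha or correlation. Back-solved as a change-score t-test (35 per arm, two-sided .05), the detectable gain is 0.679 SD of change. If half of it is lost (0.340), the interaction has expected t = 0.340 × 4.062 = 1.38. Its power is about Φ(1.38 − 1.96) = Φ(−0.58) = 0.28, so a half loss would be missed in roughly 72% of such trials.

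**Setting.** A simulation of the SAP's random-intercept model used 33 per arm, r = .7 and 300 runs, with loss coded as positive:

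- Setting shift of 0.30 SD in both arms, nothing truly lost: mean SkillJoy slope 0.29, interaction −0.02.
- True loss of 0.30 SD in SkillJoy only, no shift: mean slope 0.31, interaction 0.31.

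The slope cannot tell these cases apart. The interaction can, provided the shift is equal in both arms. The 0.30 is an assumption; the documents give neither size nor direction, so the range starts at zero.

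**The case against.** The strongest reply is that the SAP examines maintenance by comparing trajectories between arms and nowhere says that the slopes decide it, or that a null result means gains were kept. That is right. A reader might infer such a rule because the slopes sentence follows the maintenance sentence, but the text does not state it. The caution about non-significance is therefore a guard on reporting, not a correction of a stated rule.

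Second, the setting effect is hypothetical. PsychData is named at baseline and at day 30, so the documented change is of place and supervision, not of instrument. Any single-arm change also absorbs retest and time effects, which is what the randomised control is for. This stands, and it limits the setting point to a caveat.

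Third, a reader might infer that a half loss shown as a slope d can equal the d of the entire gain. The arithmetic exists: 2.031 × 0.340 = 0.69, and 1.016 × 0.679 = 0.69. But it needs slope df of 32 beside interaction df of 64. The SAP states no df, and slopes probed from one two-arm model would normally share its df. At a common df the half loss stays below the gain: 0.488 against 0.690 at df 64, and 0.345 against 0.488 at df 128. That headline is not supported.

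Fourth, the scale problem is not specific to maintenance. This is also right, and it widens the point to the slopes in every window.

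**Conclusion.** The effect-size rule is wrong as written for simple slopes. With equal arms, a common SD of change and flat controls, a slope d is 1.41 times the interaction d for the same change at any common df. The factor reaches 2.0 only if within-arm df were used, which the SAP leaves open; pooled imputation df could alter either figure. No test or p-value is affected, only the effect sizes and what is read from them.

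The change of setting is documented and cannot be separated from true change in a day-8-to-day-30 slope, nor in a pre-to-follow-up slope. Pre-to-post slopes are free of it. Between-arm contrasts are protected if any shift is equal across arms. A reader might go further and conclude that the slopes are invalid and should be discarded. The documents do not support that, because no shift is shown. Discarding also costs information: with half of a 0.68 SD-of-change gain lost, no shift and a significant pre-to-post effect, trials showing neither a significant loss nor a significant day-30 benefit would rise from about 21% to 37%.

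**What to change.** 1. Replace 2t/√df. For each outcome and window, give the within-arm changes and the between-arm difference in scale points, and again divided by one common baseline SD, all with 95% CIs. Label this as specified after data collection, since the SAP already reports the number who completed follow-up.
2. If any 2t/√df values are kept, state their df and say that slope and interaction values are not to be compared.
3. Rest the durability statement on the planned between-arm pre-to-follow-up and day-8-to-day-30 estimates with their CIs. State that a non-significant day-8-to-day-30 interaction is not evidence of maintenance.
4. If day-8-to-day-30 slopes are shown, put both arms side by side. Note that day 8 was completed in the laboratory and day 30 by emailed link, with an effect of unknown size and direction.

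The cost is effect-size code and wording, with no new model or data. Within-arm values will usually look less favourable: at df 64 and r = .5, a 0.30 SD change now prints as 0.43 and would print as 0.30. The change is also post hoc, which the label discloses.
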